8.4. Emergency Unblinding of Treatment Assignment

Not applicable.

8.5. Pregnancy

Pregnancy, in and of itself, is not regarded as an AE unless there is suspicion that study drug may have interfered with the effectiveness of a contraceptive medication or method. When a pregnancy has been confirmed, the following procedures should occur:

- The investigator must notify the sponsor or its designee immediately.
- The study drug must be discontinued immediately.

- The subject must be withdrawn from the study.
- The EOT visit evaluations must be performed.
- The investigator must complete and submit the Pregnancy Initial and Follow-Up Report forms to the sponsor or its designee.
- A serum pregnancy test must be performed to confirm the urine pregnancy test result. (The serum test should be performed at the investigative site to ensure the test will be performed promptly and the result available immediately for review.)

If a negative serum test does not confirm the urine pregnancy test result, then:

- The investigator will use his or her expert judgment, based on an assessment of the potential benefit/risk to the subject, to determine if it is in the subject's best interest to resume study drug and continue participation in the study.

To ensure subject safety, each pregnancy in a subject during maternal or paternal exposures to study drug must be reported within 24 hours of learning of its occurrence. Data on fetal outcome and breastfeeding are collected for regulatory reporting and drug safety evaluation. Follow-up to each pregnancy should be conducted to determine outcome, including spontaneous or voluntary termination, details of the birth, and the presence or absence of any birth defects, congenital abnormalities, or maternal and/or newborn complications, by following until the first well-baby visit. Pregnancy should be recorded on a Clinical Study Pregnancy Form and reported by the investigator to the sponsor or its designee. Pregnancy follow-up should be recorded on the same form and should include an assessment of the possible relationship to the sponsor's study drug of any pregnancy outcome and follow-up to the first well-baby visit. **Any SAE experienced during pregnancy must be reported on the SAE Report Form and to the sponsor or its designee.**

8.6. Warnings and Precautions

No evidence available at the time of the approval of this study Protocol indicated that special warnings or precautions were appropriate, other than those noted in the provided IB. Additional safety information collected between IB updates will be communicated in the form of Investigator Notifications (INs). Any important new safety information should be discussed with the subject during the study as needed. If new, significant risks are identified, they will be added to the ICF.

8.7. Data Monitoring Committee

A formal Data Monitoring Committee will not be used for this study. The sponsor will continuously monitor safety through frequent contact with the treating investigators, review of the clinical data, and formal study meetings. Routine teleconferences will be held among participating study sites to provide subject-by-subject updates on current study status, interim toxicities reported, and any other pertinent information. Adverse event and laboratory data entered into the clinical database will be reviewed periodically for trends and evolving safety signals. Lastly, formal review meetings will be conducted with investigators during the study to establish consensus on the safety and tolerability of a given dose.

8.8. Adverse Events of Special Interest

INCB050465 is a potent and selective PI3K δ inhibitor, which is a key target in the BCR survival pathway in normal and malignant B-lymphocytes. In animal studies, lymphoid depletion was observed and may also occur in humans. This may result in infections, fever, or cytokine release resulting in fever, chills, hypotension, wheezing, and/or rash. Reversible minimal to mild hypospermatogenesis was observed in rats at doses that exceed the intended starting clinical dose and anticipated therapeutic dose in humans. For additional information on the risks of treatment with INCB050465 and INCB039110, see Sections 1.2.3, 1.3.5, and 1.4.4.

8.9. Product Complaints

The sponsor collects product complaints on study drugs and drug delivery systems used in clinical studies in order to ensure the safety of study participants, monitor quality, and facilitate process and product improvements.

All product complaints associated with material packaged, labeled, and released by the sponsor or its designee will be reported.

The investigator or his/her designee is responsible for reporting a complete description of the product complaint and any associated AEs via email or other written communication to the Incyte contact.

If the investigator is asked to return the product for investigation, he/she will return a copy of the product complaint communication with the product.

9. STATISTICS

9.1. Study Populations

The populations to be analyzed include the following:

- **Intent-to-treat (ITT) population/safety population:** Subjects enrolled in the study who received at least 1 dose of INCB050465, INCB039110, rituximab, ifosfamide, carboplatin, and/or etoposide.
- **Per-Protocol (PP) population:** Subjects in the ITT/safety population who are sufficiently compliant with the Protocol. Details will be provided in the SAP.
- **PK [REDACTED] population:** Subjects in the ITT/safety population who had PK [REDACTED] data.

The ITT/safety population will be used for the summary of baseline, disposition, efficacy, and safety analyses. The PP population may be used in the sensitivity analysis of efficacy endpoints. The PK [REDACTED] population will be used in the summary of all PK [REDACTED] data.

9.2. Selection of Sample Size

The total sample size estimate is up to approximately 150 subjects in this study. Approximately 20 subjects will be enrolled in Part 1 monotherapy dose escalation, and approximately 12 subjects will be enrolled in Part 2 combination dose escalation. Expansion Cohort A will enroll between 15 and 30 subjects, and Cohorts B, C, D, and E will enroll up to 15 subjects each.

In Part 6, up to 12 subjects will be enrolled in the safety evaluation followed by an expansion cohort of up to 15 subjects. The exact number of subjects treated will depend on the number of subjects required per dose level and the number of dose levels studied. During the 3 + 3 dose escalation in Part 1 and Part 2, the probabilities of dose escalation from that dose level for various DLT rates are given in [Table 13](#).

Table 13: Probability of Dose Escalation for Specific Dose-Limiting Toxicity Rates During 3 + 3 Dose Escalation

True DLT Rate	Probability of Dose Escalation
10%	90.6%
20%	70.9%
30%	49.4%
40%	30.9%
50%	17.2%
60%	8.2%

Note that if escalation occurs at the highest dose level during the study, then the MTD is at or above the last dose level. If the study stops at the first dose, then the MTD is below the first dose level. In either of these cases, the prescribed doses may need to be altered in order to determine the MTD.

In the expansion cohorts the evaluation of 15 subjects, each will provide a $\geq 90\%$ chance of identifying a toxicity with a true event rate of 15%.

9.3. Level of Significance

No hypothesis is being tested in the study. All CIs will be 95%.

9.4. Statistical Analyses

9.4.1. General Methodology

Unless otherwise noted, SAS® software (SAS Institute Inc, Cary, NC; Version 9 or later) will be used for the generation of all tables, graphs, and statistical analyses. Descriptive summaries for continuous variables will include, but not be limited to, the number of observations, mean, standard deviation, median, minimum, and maximum. Descriptive summaries for categorical variables will include the number and percentage of subjects in each category.

Data will be summarized overall and by treatment cohorts based on the dose regimen initially assigned. In the event that several dose regimens tested are deemed substantially below the MTD, these doses may be combined for summary purposes.

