5.7. Withdrawal of Subjects From the Study

5.7.1. Withdrawal Criteria

Subjects **must** be withdrawn from the study for the following reasons:

- Further participation would be injurious to the subject's health or well-being, in the investigator's medical judgment.
- The subject becomes pregnant.
- Consent is withdrawn.
- The study is terminated by the sponsor.
- The study is terminated by the local health authority or IRB or IEC.
- Unacceptable toxicity has occurred (see Section 5.6.2.1).
- Disease progression has occurred (see [Appendix D](#), [Appendix E](#), or [Appendix F](#) for definition) except
 - in the circumstance where, in the setting of otherwise stable disease, a medical procedure or radiation therapy is required to a single lesion, with medical monitor approval, or
 - if progression is observed on a once-weekly schedule after an objective response was observed on a QD schedule, a subject may be returned to the QD schedule if it is determined to be in the subject's best interest by the investigator (eg, no better

alternative) and agreed by both the subject and the medical monitor. The subject should be withdrawn when a subsequent radiological assessment demonstrates further deterioration or sooner based on clinical signs and symptoms.

- Note: Subjects receiving INCB039110 monotherapy study treatment may receive combination therapy with INCB039110 and INCB050465 as described in Section 4.2.

A subject **may** be withdrawn from the study as follows:

- If, during the course of the study, a subject is found not to have met eligibility criteria, the medical monitor, in collaboration with the investigator, will determine whether the subject should be withdrawn from the study. Refer to Section 11.3, Protocol Adherence.
- If a subject is noncompliant with study procedures or study drug administration in the opinion of the investigator, the sponsor should be consulted for instruction on handling the subject.

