9.4.2. Efficacy Analyses

[figure not shown]
The efficacy endpoints will be analyzed using the ITT and the PP populations.

Response status per investigator's assessment will be categorized at each response assessment visit as CR, very good partial response (VGPR; only among subjects with WM), partial response (PR), minor response (MR; only among subjects with WM), stable disease (SD), progressive

disease, or not evaluable (NE) per published criteria for lymphoma (Cheson et al 2014, Owen et al 2013 for WM) and CLL (Hallek et al 2008, Cheson et al 2012). In the unlikely situation that the subject does not have any disease at baseline, the best response will be denoted as no disease (ND).

Best overall response is the best response recorded during the study treatment before and including the first progressive disease, in the order of CR, PR, SD, progressive disease, NE, and ND.

A subject is considered an objective responder if they have a best overall response of CR or PR for lymphoma or CR, VGPR, PR, or MR for WM. The ORR is the proportion of objective responders. Subjects who do not have sufficient baseline or on-study response assessment information to be adequately assessed for response status will be included in the denominators in the calculation of ORR. ORR will be estimated with 95% CI, which will be calculated based on the exact method for binomial distributions. Best overall response will also be summarized.

For subjects with CLL, changes in peripheral blood leukemic cells from baseline to each post-treatment assessment will be summarized with mean, median, standard error, and 95% CIs.

For subjects with measurable lesions, target lesion sizes will be measured by sum of product of diameters (SPD). The best percent change from baseline, defined as the largest decrease in SPD during study will also be summarized, and a waterfall plot of best percent change will be generated. Note that for subjects who only have increases in SPD from baseline, the smallest increase will be considered as the best change from baseline.

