9.4.3. Safety Analyses

The clinical safety data (vital signs, ECGs, routine laboratory tests, physical examinations, and AEs) will be summarized using descriptive statistics (eg, mean, frequency) using the safety population.

Summary tables may be replaced with listings when appropriate. For instance, an AE frequency table may be replaced with a listing if it only contains a few unique preferred terms reported on

relatively few subjects. Unless otherwise stated, table summaries will be limited to AEs occurring within 30 days of the last administration of study medication.

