## **6.4. Exposure**

For subjects in the safety population, duration of treatment, average daily dose (mg), and dose modifications will be summarized descriptively. The summaries will be provided separately for

INCB050465 and INCB039110 when applicable. Administrations of the study drug will be listed.

- **Duration of treatment:** The number of study days from Day 1 to the last day of INCB050465 or INCB039110 taken by the subject.
- **Average daily dose (mg/day):** Total dose taken by the subject divided by duration of treatment in days.
- **Dose modifications:** Number of subjects who had dose reduction, interruption, and escalation will be summarized.

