### **7.2.2. Best Overall Response and Overall Response Rate**

[figure not shown]
Best overall response is the best response recorded during the study treatment prior to and including the first PD, in the order of CR, VGPR, PR, MR, SD, PD, and NE. In the case of SD, assessment must meet the SD criteria at least once on or after Day 42. Subjects who fail to meet this criterion will have best response of PD if the next available assessment after the initial assessment indicates PD or will have best response of NE if there are no additional assessments available.

A subject is considered a responder if they have a best overall response of CR or PR (CR, VGPR, PR, or MR for subjects with WM postbaseline).

The ORR is the proportion of responders. Subjects who do not have sufficient baseline or on-study response assessment information to be adequately assessed for response status will be included in the denominators in the calculation of ORR.

Best overall response will be summarized descriptively. The ORR will be estimated with 95% CIs. Confidence intervals will be calculated based on the exact method for binomial distributions.

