#### **7.2.5. Best Change in Target Lesion Size**

For subjects with measurable lesions at baseline, target lesion sizes will be measured by sum of product of diameters. The best percentage change from baseline, defined as the largest decrease in target lesion sizes during the study, will be summarized, and a waterfall plot of the best percentage change will be generated. Note that for subjects who only have increases in target lesion sizes from baseline, the smallest increase will be considered as the best change from baseline.

Target lesions considered "too small to measure" will be assigned a default value of 5 mm × 5 mm for purposes of this analysis. Likewise, target lesions identified as "not present" at postbaseline assessments will be assigned 0 mm for this analysis. In the event that a target lesion is unaccounted for in a particular postbaseline timepoint (ie, the assessment is missing or NE), then the overall sum of target lesions will not be evaluable for that postbaseline timepoint.

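### Best change in target lesion size has no stop at first progression, unlike best overall response, so shrinkage after progression or local therapy can enter the waterfall; crossover subjects also lack a stated analysis rule

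*Protocol*

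**What the plan says.** Two response summaries have different time windows. Best overall response is limited in both documents; SAP 7.2.2 states "Best overall response is the best response recorded during the study treatment prior to and including the first PD", and Protocol 9.4.2 has the same limit. Best SPD change has none. Protocol 9.4.2 has "The best percent change from baseline, defined as the largest decrease in SPD during study will also be summarized", and SAP 7.2.5 has "The best percentage change from baseline, defined as the largest decrease in target lesion sizes during the study, will be summarized".

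SAP 7.2.5 also fixes how awkward lesions are scored. A target lesion recorded as not present counts as 0 mm. One too small to measure counts as 5 mm by 5 mm. If any target lesion is missing or not evaluable at a visit, the sum is not evaluable at that visit.

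Protocol 5.7.1 requires withdrawal at progression, with two exceptions. The first applies when disease is otherwise stable and "a medical procedure or radiation therapy is required to a single lesion, with medical monitor approval". The second is "if progression is observed on a once-weekly schedule after an objective response was observed on a QD schedule, a subject may be returned" to daily dosing, if the investigator, subject and medical monitor agree.

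The synopsis and Protocol 4.2.5 also let monotherapy subjects cross over to a combination. The grouping rule in Protocol 9.4.1 is "Data will be summarized overall and by treatment cohorts based on the dose regimen initially assigned". For safety, Protocol 9.4.3 adds "Unless otherwise stated, table summaries will be limited to AEs occurring within 30 days of the last administration of study medication"; SAP 8.1 agrees. SAP 4.1.3 sets one baseline, before the first dose of any study treatment.

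**The concern.** The waterfall will be read as a picture of what the starting regimen did. With an open window, a scan taken after progression counts in full, even if the lesion shrank because it was irradiated or removed. The display would then overstate the regimen's activity and could show a deep bar for a subject whose best overall response is stable or progressive disease. Such a mismatch can also arise legitimately, for example when new lesions appear while target lesions shrink. From the figure alone, nobody could tell which cause applied.

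Crossover raises a related question for the primary endpoint, safety. If a crossover subject stays one record under the starting regimen, adverse events that begin on a combination are tabulated as monotherapy events.

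**Working it through.** The documents give no figure on this point, so there is none to reproduce. The check compares the rules and then works an assumed case.

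**1. Windows.**
- Best overall response: on treatment, up to and including first progression (Protocol 9.4.2, SAP 7.2.2).
- Best SPD change: during the study, no stop at progression, local therapy or crossover (Protocol 9.4.2, SAP 7.2.5).
- Adverse-event tables: to 30 days after the last study medication, no stop at crossover (Protocol 9.4.3, SAP 8.1).

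Scans taken under either exception in Protocol 5.7.1 therefore fall outside the first window and inside the second.

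**2. Local therapy after progression (lesion sizes assumed).** Two target nodes, each 4.0 x 2.5 = 10.0 cm², give a baseline SPD of 20.0.
- Nadir: each 3.0 x 3.0 = 9.0, SPD 18.0; 18.0/20.0 - 1 = -10%, stable disease.
- Progression: node 1 at 4.5 x 3.0 = 13.5; 13.5/9.0 - 1 = +50%, which meets the product criterion in Protocol Appendix D. SPD is 22.5; 22.5/20.0 - 1 = +12.5%. The diameter increase is 1.5 cm. The minimum for lesions over 2 cm is not legible in the text at hand, so I assume this suffices.
- Node 1 is irradiated and recorded as not present; node 2 stays at 9.0. SPD is 9.0; 9.0/20.0 - 1 = -55%.

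Best overall response is stable disease. Cut at progression, best SPD change is -10%. As written it is -55%, past the 50% fall used for partial response in Appendix D.

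**3. How the lesion is recorded.** Too small to measure: 0.5 x 0.5 = 0.25 cm², SPD 9.25; 9.25/20.0 - 1 = -53.75%. Not evaluable: no sum at that visit, and the bar stays at -10%. No visible text says which recording applies to a treated lesion.

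**4. Range.** With both nodes at 90% of baseline and a treated share s of baseline SPD, the plotted change is 0.9(1 - s) - 1. This gives -19% at s = 0.1, -55% at s = 0.5 and -91% at s = 0.9. It reaches -50% at s = 1 - 0.5/0.9 = 44.4%.

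**5. Return to daily dosing.** This route requires an earlier objective response, so it can only deepen a responder's bar.

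**6. Crossover, if one record.** In a 15-subject cohort, each subject with an event only on the combination adds 1/15 = 6.7 percentage points to its monotherapy incidence; three add 3/15 = 20.0. Protocol 1.4.2 reports 3 subjects on the INCB039110 combination by 02 SEP 2016, so between 0 and 3 crossovers to it by then. Under a two-record reading, the subject counts twice in the overall column, and the SAP 4.1.3 baseline does not fit the second record.

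**The case against.** SPD change is not a listed endpoint, no hypothesis is tested, and all analyses are exploratory. The local-therapy exception needs otherwise stable disease, a single lesion and medical monitor approval, so few subjects will qualify. A treated lesion may be recorded as not evaluable, which removes the visit. Listings 2.6.2 and 2.6.3 let a careful reader trace any mismatch. SAP 7.2.3 and 7.2.4 are not visible and parts of Protocol 9.4 are blacked out, so a cut-off rule may exist there. All of this limits the size of the problem; none of it supplies the missing stop in the visible text.

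Three stronger readings are tempting, and the documents do not support them.

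- **That the plan pools combination data under monotherapy.** Protocol 4.2.5 has the subject enroll in the combination, meet that cohort's eligibility criteria, and count the earlier drug as prior PI3K inhibitor use. Protocol 5.6.3 and 5.7.2 call for withdrawal and an end-of-treatment visit. Exclusion 2 asks for a washout of 28 days or 5 half-lives unless the medical monitor approves otherwise. A new enrollment is the more natural reading, though no passage says so. Causality is recorded per agent (Protocol 8.1.1), and SAP 8.2.3 plans INCB039110-related tables. These separate some events but do not cut the all-event tables.
- **That SAP 6.4 merges exposure to the two drugs.** Its definition is "The number of study days from Day 1 to the last day of INCB050465 or INCB039110 taken by the subject", but the same section summarizes the drugs separately, as does shell Table 3.1.1.
- **That SAP 5.2 (by disease subtype) conflicts with the dose-group columns.** The Waldenström version of shell Table 2.2.1 shows the intended layout: one table per subtype, with dose groups as columns.

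**Conclusion.** The window mismatch holds on the visible text: following both documents as written can put shrinkage after progression or local therapy into the waterfall. Severity is minor. The number of subjects who continued after progression or crossed over is not given, so the bias cannot be computed. The -55% and the -19% to -91% range are illustrations that rest on assumed lesions and on the treated lesion being recorded as not present.

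The crossover point is secondary and conditional: it does harm only under a one-record reading, which is possible but less natural. Cycle 1 dose-limiting toxicities are unaffected. The cut at first progression protects the response rate whenever crossover follows progression. It would not do so for a one-record subject who crossed over for another reason. The synopsis describes crossover at progressive disease, whereas Section 4.2.5 refers to any withdrawal reason in Section 5.7.1; these passages must be reconciled.

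**What to change.** - In SAP 7.2.5, end SPD-change evaluation at the earliest of first progression, local therapy to a target lesion, or the first dose of a crossover combination. The local-therapy stop is needed separately in case a treated lesion was never recorded as progression. Put later lesion data in a listing.
- State whether a crossover subject is one analysis record or two, and how the overall column counts that subject.
- End the monotherapy window for treatment-emergent events at the first combination dose, and summarize the crossover period separately with its own baseline. Keep the tables by initial assignment as the main display.
- Reconcile the crossover wording in the synopsis and Protocol 4.2.5.

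The cost is SAP wording and programming. The case report form already collects lesion assessments, adverse events, study drug administration and concomitant procedures, although collection is reduced after Amendment 10. The drawbacks are that shrinkage after progression leaves the main waterfall, the monotherapy columns lose some follow-up, and late monotherapy toxicity that first appears after crossover moves to the crossover group.

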4.2.5. Crossover to Combination Therapy After Monotherapy Treatment

For subjects who discontinue INCB050465 monotherapy for a reason described in Section 5.7.1, the investigator may feel that the best option for the subject is to enroll in a combination therapy offered in this Protocol. Prior use of a PI3K inhibitor is not prohibited per the inclusion/exclusion criteria for combination cohorts. Therefore, subjects who discontinue INCB050465 may be allowed to cross over to combination therapy. In these cases, the subject must meet the eligibility criteria for the cohort they will cross over to, and the sponsor must approve the crossover.

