5.4. Duration of Treatment and Subject Participation

Subjects in Parts 1, 2, and 3 will be treated in continuous 21-day cycles indefinitely; this may include temporary interruptions described in Section 5.6. Subjects in Part 6 will be treated in 21-day cycles. INCB050465 may continue indefinitely, but R-ICE will only be given for 3 cycles.

Subjects who have evidence of objective clinical benefit, regardless of dose level, may continue to be treated at that dose level. Dose and schedule changes may be implemented for ongoing subjects based on emerging tolerability data. If study drug is permanently discontinued (for reasons, see Section 5.6.2.1) the subject will be withdrawn from the study. Treatment duration will vary among subjects, but is expected to average approximately 6 months.

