5.5. Rationale for Dose Modification

Selections and modifications to the dosage of study drug are planned for dose-escalation cohorts. Also, dose interruptions and modifications may occur for individual study subjects. The identification of DLTs will define the doses used in planned cohorts. Further, the occurrence of DLTs and other toxicities will guide decisions for treatment interruptions and discontinuation for individual subjects.

Subjects enrolled in lower doses in the dose-escalation portion of the study will have the option of escalating to a dose found to be tolerated in a subsequent cohort provided the criteria specified in Section 5.6.1 are met.

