5.6. Dose Adjustment of Study Drug

5.6.1. Planned Dose Adjustments

Cohort dose escalation is described in Section 4.1. Intrasubject dose escalation of INCB050465 will be allowed during dose escalation, provided that the following criteria are met:

- The Protocol inclusion criteria are met.
- The subject has received 4 cycles of study drug and has not had a related or possibly related toxicity \geq Grade 2.
- The next dose level has been determined to be safe based on DLT rules (eg, no DLTs during Cycle 1).
- The subject is willing to submit to all visits and procedures as in Cycle 1 per the Protocol, except the PK [REDACTED] sampling will only be done as on Cycle 1 Day 15 (Day 1 and Day 8 PK [REDACTED] sampling will not be done).
- In the opinion of the investigator, the subject does not have any concurrent condition or circumstance that would complicate the dose escalation or PK sampling, or pose increased risk to the subject.
- The intrasubject dose escalation has been approved by the sponsor.

5.6.2. Criteria and Procedures for Dose Interruptions and Dose Reductions of INCB050465 and INCB039110

In some circumstances, it may be necessary to temporarily interrupt treatment as a result of adverse experiences that may have an unclear relationship to study drug. Treatment with INCB050465, the combination with INCB039110, or the combination with standard therapies may be delayed up to 2 weeks to allow for resolution of toxicity. If treatment needs to be interrupted in subjects receiving the combination of INCB050465 and INCB039110 for toxicities with unknown causality, both study medications should be held. However, based on the evolving experience with the study treatments, the suspected causal agent only may be held (while the other study treatment continues) until resolution of toxicity following consultation and approval with the medical monitor. Subjects may resume treatment if no medical condition or other circumstance exists that, in the opinion of the investigator, would make the subject unsuitable for further participation in the study. The treating investigator should contact the sponsor's medical monitor to discuss the case of any subject whose treatment has been delayed for more than 14 days before treatment with INCB050465 or the combination of INCB050465

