### **5.2. Treatment Groups**

This is a Phase 1, open-label, dose-escalation study; therefore, there are no randomized treatment groups.

The efficacy endpoints, including ORR, [REDACTED] and change in target lesion size, will be summarized by disease subtype. Change in peripheral blood leukemic cells will only be analyzed for subjects with CLL. All other data, including baseline and safety, will be summarized by dose groups. In the event that several dose regimens tested are deemed substantially below the MTD, these doses may be combined for summary purposes.

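### By-dose safety tables credit events that begin after a dose or schedule change to the starting regimen, and no table by regimen at onset is planned

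*Protocol*

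**What the plan says.** Protocol Section 9.4.1 gives the general tabulation rule: "Data will be summarized overall and by treatment cohorts based on the dose regimen initially assigned". It states no exception for subjects whose regimen later changes. SAP Section 5.2 puts efficacy by disease subtype and then says "All other data, including baseline and safety, will be summarized by dose groups". It does not say whether a dose group means the starting dose or the current one, or whether schedule counts.

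The protocol provides for regimen changes within a subject:

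- Section 5.5: subjects enrolled at lower doses in the escalation "will have the option of escalating to a dose found to be tolerated in a subsequent cohort".
- Section 5.6.1: "Intrasubject dose escalation of INCB050465 will be allowed during dose escalation, provided that the following criteria are met". One criterion begins "The subject has received 4 cycles of study drug and has not had a related or possibly related toxicity" and sets the limit at Grade 2 or higher. Sponsor approval is also needed.
- Section 5.4: "Dose and schedule changes may be implemented for ongoing subjects based on emerging tolerability data".
- Section 5.7.1: after progression on the once-weekly schedule following a response on QD, "a subject may be returned to the QD schedule".

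The AE summaries run to 30 days after the last dose (Protocol Section 9.4.3, SAP Section 8.1), so they include time on the later regimen.

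**The concern.** If the column label is the starting regimen and the counting window covers all treatment, an event that begins on the second regimen is reported as an event of the first. Two distortions follow. A low-dose subject who escalates and then has a toxicity adds it to the low-dose column. A QD subject moved to once-weekly dosing adds lower-intensity time to the QD column, so long-term QD looks safer than it is if weekly dosing is less toxic.

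The primary objective includes selecting doses for further evaluation. Sections 4.2 and 4.2.3 say the monotherapy expansion cohorts may explore several doses and schedules to obtain long-term safety data. Section 1.7.1 proposes the once-weekly phase because it may lower the frequency of AEs. The by-dose and by-schedule safety tables are where a reader would look for that.

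**Working it through.** The plan states no figure for this point, so the check compares the rules and then illustrates size.

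**1. Does any visible table correct the attribution?** SAP Section 6.4 promises a count of subjects with dose escalation. Shell 3.1.1 has rows for interruption and reduction but none for escalation. SAP Section 8.2.3 and the Appendix A table list contain nothing by dose or schedule at onset, and nothing that stops at a change. Some text is redacted, so absence is judged on what is visible.

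**2. Does the timing allow it?** Inputs are from Protocol Section 1.2.4 (data of 02 SEP 2016).

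- Earliest escalation: 4 × 21 = 84 days. Median treatment duration was 104 days, so at least half of the 46 subjects, over all dose levels, were treated past that time.
- AE discontinuations: 11/46 = 24%, with all but 1 of the events after the 9-week assessment (day 63). Late toxicity falls largely where regimens can change.
- The escalation criterion excludes anyone with an earlier related or possibly related toxicity of Grade 2 or higher. If it is applied up to the escalation itself, every such event in an escalated subject begins after the change and is still credited to the lower dose.

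**3. Low-dose column (assumed rates).** Let p1 be the AE risk at the starting dose, f the share of AE-free subjects who change dose, and p2 their AE risk at the later dose. The booked rate is 1 − (1 − p1)(1 − f·p2). With p2 = 24–35% and f = 10–50%:

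- p1 = 10%: from 1 − 0.90 × 0.976 = 12% to 1 − 0.90 × 0.825 = 26%.
- p1 = 15%: from 1 − 0.85 × 0.976 = 17% to 1 − 0.85 × 0.825 = 30%.

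**4. QD versus once weekly (assumed rates).** Let pQ be the AE-discontinuation risk on QD over the 24 weeks after Week 9. The weekly hazard is r times the QD hazard, and all ongoing QD subjects switch s weeks after Week 9 (Week 17 or 21). With h = −ln(1 − pQ)/24, the weekly risk is 1 − exp(−24·r·h) and the risk shown under QD is 1 − exp(−[s + (24 − s)·r]·h).

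| pQ | r | s | Weekly risk | Risk shown as QD | True difference | Apparent difference |
|---|---|---|---|---|---|---|
| 30% | 0.25 | 8 | 8.5% | 16.3% | 21.5 | 7.8 |
| 30% | 0.25 | 12 | 8.5% | 20.0% | 21.5 | 11.5 |
| 30% | 0.50 | 8 | 16.3% | 21.2% | 13.7 | 4.8 |
| 30% | 0.50 | 12 | 16.3% | 23.5% | 13.7 | 7.1 |
| 40% | 0.25 | 8 | 12.0% | 22.5% | 28.0 | 10.6 |
| 40% | 0.25 | 12 | 12.0% | 27.3% | 28.0 | 15.3 |
| 40% | 0.50 | 8 | 22.5% | 28.9% | 17.5 | 6.3 |
| 40% | 0.50 | 12 | 22.5% | 31.8% | 17.5 | 9.3 |

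If only half of the QD subjects are switched, the apparent difference is the average of the last two columns: 9.2 to 21.7 points over the eight rows.

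**5. Response.** Of 18 NHL responses, 17 (94%) were seen by the first assessment, scheduled at 9 weeks and so before the 12-week escalation minimum. Best overall response also stops at first progression (Section 9.4.2), so a response after return to QD following progression is not counted.

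**The case against.** Five arguments limit the point.

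- **Scope.** A reader might infer from Section 9.4.1 that every table is distorted. That is too broad. DLTs are Cycle 1 only, before any escalation is allowed. Exposure uses the dose actually taken. PK parameters are compared by dose level. SAP text groups efficacy by disease subtype, although the shells carry dose columns. Where the assigned regimen is 20 mg QD for 9 weeks and then once weekly, the label is right and only the split between phases is lost.
- **Dose selection.** Decisions rest on Cycle 1 DLTs plus all safety data to date (Section 5.5.1) and subject-by-subject review (Section 8.7). No hypothesis is tested, and Section 4.4 disclaims comparisons between subjects. So the documents do not support saying that dose selection is compromised. What remains is the safety reading that a report by dose and schedule invites.
- **Size.** The 5, 10 and 15 mg groups had 1, 3 and 3 subjects, so one event moves a rate by 33 to 100 points, or by 1/7 = 14 points if all three are combined. That is mostly small denominators, and it holds under any attribution rule. It does not measure this effect.
- **Direction.** A reader might infer that a contrast could reverse. The schedule model gives shrinkage only: in every row the risk shown as QD stays above the weekly risk.
- **Remedy.** Making an on-regimen table the main one has its own bias. Escalators are selected for tolerance, windows become unequal, and late toxicity from QD may surface on weekly dosing.

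All five stand as limits. None explains why no supportive view exists.

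**Conclusion.** The concern holds for safety data. Under Section 9.4.1, TEAEs and laboratory values that arise after an intrasubject escalation or a change of dose or schedule are credited to the starting regimen, SAP Section 5.2 leaves its grouping undefined, and no visible table shows the regimen at onset. Low doses can look more toxic, and a QD versus once-weekly difference can shrink.

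The size depends on how many subjects change regimen and when, which the documents do not give; they do not show that anyone escalated. The figures in steps 3 and 4 rest on assumed risks, constant hazards and a stated share of switchers. They show that the effect could matter, not how large it is here. The effect on response is likely small.

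Grouping by initial assignment is a legitimate view. The gap is that it is the only one.

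**What to change.** In SAP Section 5.2, define dose group as the regimen initially assigned, in line with Protocol Section 9.4.1, and keep those tables.

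Add three supportive by-dose tables (TEAEs, SAEs and AEs leading to discontinuation) by regimen, meaning dose and schedule, at onset. Give exposure-adjusted rates: events or subjects per unit of patient-time on that regimen. Handle all dose changes, reductions included, by the same rule. In the response summary or listing, flag responses first recorded after an escalation or schedule change.

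The cost is SAP wording and programming, since dosing records are already collected and listed (SAP Section 6.4). There are two downsides. A subject can appear in more than one column. Post-change columns hold subjects selected for having tolerated earlier treatment, with possible carry-over of late toxicity. Label these tables supportive and say why in a footnote.
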